2) The Blood Connection (TBC) is located in Piedmont, SC with a satellite in Raleigh, NC and was established in 1962. The Blood Connection is registered and licensed by the US FDA and accredited by the American Association of Blood Banks. TBC has two blood mobiles, which travel throughout the Triangle and one fixed site where blood is collected and products are produced. Blood collection is performed by single whole blood donation and automated apheresis for the collection of red cell, plasma and platelets. TBC (Raleigh) processes approximately 18,000 donations per year, manufactures red blood cell products, frozen plasma products, and platelet products; in North Carolina TBC is the primary supplier to Wake Med and Rex Hospitals in Raleigh. They also supply Duke University Medical Center, as inventory and need allows, especially for autologous units. The VP Business Development/Chief Technical Officer of TBC ([name]) and the medical director ([name]) has agreed to allow the blood collections and processing for this study to take place at TBC using their standard procedures for autologous blood collection by apheresis. A fee is being charged to Duke for these services as if this were a standard autologous donation.

Study size:

In this pilot study, we will plan to enroll 20 subjects.

Eligibility Criteria:

Healthy, habitually exercising, non-smoking, non-diabetic males and females (as described in the inclusion/exclusion criteria below):

Qualified volunteers will be enrolled at a single center (Duke University Medical Center). After subjects provide written informed consent, eligibility will be confirmed with a questionnaire and screening tests (below). We have used these methods before, and they are designed, in large part, to insure the safety of participants.

Inclusion Criteria:

- i. Healthy male or female
- ii. Age 18-40 (the American College of Sports Medicine Guidelines for Exercise Testing defines this age group with no or no more than one coronary heart disease risk factor as low-risk for VO₂ max testing)
- iii. Habitual exerciser defined as ≥ 30 minutes of at least moderate or high intensity exercise ≥ 3 times per week. After consent, and at the subsequent screening visit, a VO₂ max test will be performed, and subjects with a low value (< 30 mL/kg/min) will be excluded (screen failure). Based on our

RESEARCH Summary

Pro00078468

NCT03089047

PI: [name]

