previous experience, we anticipate that up to 25% of the subjects will fall into this category; therefore, 20 subjects will be screened to obtain 10 participants who go on to donate their blood.

- iv. Calculated total blood volume of at least 4,500 mL using an established formula:

- a. Men: $(0.006012 \times H^3) + (14.6 \times W) + 604 = TBV$
- b. Women: $(0.005835 \times H^3) + (15 \times W) + 183 = TBV$

[H= Height in inches; W=Weight in pounds]

- v. Has access to transportation to visit the blood collection facility and to return to Duke for all study visits
- vi. Weighs at least 130 pounds

Exclusion Criteria:

- i. Any significant acute or chronic medical illness or problem, including, but not limited to, diabetes, hypertension, cardiac disease, asthma, COPD
- ii. Current or recent (last 60 days) tobacco or nicotine use
- iii. History of sickle cell trait or disease or any other acquired or hereditary hematological abnormality
- iv. History of fainting or other significant adverse reaction during phlebotomy or donation of blood
- v. Known prolonged QTc (or evidence of such at screening) defined as QTc >470 ms
- vi. Known or suspected illicit drug or alcohol abuse
- vii. Known or suspected HIV, Hepatitis B, or Hepatitis C infection
- viii. History of thrombophilia or anticoagulant therapy
- ix. Pregnancy
- x. Obesity defined as BMI>30
- xi. Recent history of blood donation:
 - a. Single whole blood unit donation within the past 8 weeks
 - b. Double RBC donation by apheresis within the past 16 weeks
 - c. Plasma donation by apheresis within the past 4 weeks
 - d. Any self-reported blood donation within a year
- xii. Inadequate red blood cell mass evidenced by total blood volume <4500 mL (above) or screening hemoglobin <13.3 g/dL
- xiii. Known hypersensitivity to lithium compounds. And known taking lithium salts for treatment of other medical/psychiatric conditions

RESEARCH Summary

Pro00078468

NCT03089047

PI: [name]

xiv. Students and employees who are under direct supervision of the investigators

Study structure: study visits (A-E).

A	Screen	Screen, consent, H&P, ECG, screening labs, and VO ₂ max
B	Day 0	Donate 2 units of PRBCs by autologous apheresis
C	Day 14	8am Measure pre-transfusion, “anemic” VO ₂ max 9 am Transfuse 2 units of standard or rejuvenated PRBCs 3 pm Measure post-transfusion VO ₂ max (end of study)

listed in this study.

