7. Subject Identification, Recruitment, and Compensation: Healthy volunteers who respond either to our advertisement or by word of mouth will be shown the eligibility criteria and asked if they believe they are likely to be eligible. Volunteers who responded to advertisement and left their phone numbers in voicemail will be returned call by investigator/delegated key personnel. Investigator/ designee will use IRB-approved phone script as reference to discuss the study activities over the phone and at the same time ask permission to PHI use prior to written consent form. Volunteers who ended up enrolling in the study but are screen failures (after lab results out) will be compensated \$100. Participants will received up to total of \$1000 by completion of all study activities, inclusive of screening visit and blood donation . Volunteers who has donated blood and missed subsequent visits will be compensated \$100 for that specific visit. In addition, subjects will be provided with supplemental oral fluids (juices) and a light snack on day 14 during the break after the autologous blood transfusion and before the second exercise testing .

A member of the study team will conduct the consent process in an office at Duke Medical Center. He/she will describe the study and ask the volunteer to read the consent form and ask any questions they may have. As much time as the subject needs will be provided for conducting the consent process, and the potential subject will have as much time as they need to consider whether or not to participate.

RESEARCH Summary

Pro00078468

NCT03089047

PI: [name]

8. Costs to the Subject: Subjects will incur no direct costs as a result of this study. Subjects will only be responsible for indirect costs such as parking fees.

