Preliminary data also show that the variability of $VO_{2\max}$ has a narrow range, with standard deviation ranging from $0.8-1.9$ for a given subject ([name], personal communication). Combining with our preliminary data (which showed an increase after transfusion of $2.4 \pm 0.6 \text{ ml/kg/min}$ – see above), we set our standard deviation for the power analysis (σ) at $\pm 1.5 \text{ mL/kg/min}$.

Using this data, we can expect 80% power to detect a significant ($p < 0.05$) intergroup difference in the change in $VO_{2\max}$ from anemic to post-transfusion state with 3 volunteers in each group. More patients will be studied as unexpected variability may occur.

10. Data & Safety Monitoring: We will record and analyze both expected and unexpected adverse events in order to monitor for and minimize potential risks to

RESEARCH Summary

Pro00078468

NCT03089047

PI: [name]

human subjects. Adverse events that occur during any study procedure will be collected and reported to the IRB, and FDA as appropriate. The Principal Investigator will review serious and non-serious AEs on a rolling basis as well as in aggregate on a monthly basis. Given the long standing safety of VO₂ max testing as well as blood collection and transfusion studies (many removing far larger volumes of RBCs) we do not expect to see a significant number of adverse events.

11. Privacy, Data Storage & Confidentiality: Study records that identify the patient will be kept confidential as required by law. They will be kept in a locked file cabinet in either the Study Coordinator's or [name] office. Data will also be stored in password protected computers. Except when required by law, the subject will not be identified by name, social security number, address, telephone number, or any other direct personal identifier in study records disclosed outside of Duke University Health System (DUHS). The results of this research study may also be presented at meetings or in publications; however, identity will never be disclosed in those presentations. In no way will any subjects' name be used in any published form.

As part of the study, [name] and the study team will report the results of the study-related laboratory tests named below. These test results will be recorded in the study record and results of tests and studies done solely for this research study will not be included in the volunteer's medical record.

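### The numbers screened, enrolled, donating and powered are not reconciled, no number to be randomised is stated, and the 80% power claimed at 3 per group does not hold for the planned t-test

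*Combined protocol and SAP*

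**What the plan says.** All references are to the combined protocol and SAP.

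- **Section 4, Study size:** "In this pilot study, we will plan to enroll 20 subjects".
- **Section 4, Eligibility Criteria (opening text):** "Qualified volunteers will be enrolled at a single center". Here, enrolment seems to follow qualification.
- **Section 4, Inclusion Criteria iii:** after a screening VO₂max test, "subjects with a low value (< 30 mL/kg/min) will be excluded (screen failure"). The plan then expects that "up to 25% of the subjects will fall into this category; therefore, 20 subjects will be screened to obtain 10 participants" who donate.
- **Section 4, Exclusion Criteria:** several other grounds can also remove a subject at screening, for example "Inadequate red blood cell mass evidenced by total blood volume <4500 mL (above) or screening hemoglobin <13.3 g/dL". No expected rate is given for any of them.
- **Section 7:** "Volunteers who ended up enrolling in the study but are screen failures" are paid a fixed sum. Here, enrolment comes before the screening result.
- **Section 9:** the primary comparison is a two-group t-test at two-sided 0.05, or a rank-sum test if the data are not normal. The assumed difference is 3.5 ml/kg/min and the SD is 1.5 ml/kg/min. The plan claims 80% power "with 3 volunteers in each group", and adds: "More patients will be studied as unexpected variability may occur".
- **Section 9, on timing:** randomisation is on Day 14, after donation, and subjects lost before then are dropped from the analysis.

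**The concern.** Three things do not fit together.

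First, the number of donors is presented as a consequence of the 25% failure rate, and it does not follow from that rate.

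Second, a reader cannot find the number to be randomised. The 20 may be people screened or people who qualified. The 10 are donors, who could still be lost before Day 14. The 3 per group is a figure for power, with an unspecified number to be added.

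Third, the one sample size that carries a power statement does not have that power under the test the plan names, and the size the plan seems to be heading for (10 donors) has no power statement.

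At stake is whether the trial has a defined end and a correct power figure for its primary comparison. A trial that stopped at the size described as giving 80% power would have a type II error of about 42% rather than 20%, if the plan's own assumptions were true.

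**Working it through.** **Inputs.** From Section 9: difference δ = 3.5, SD σ = 1.5, two-sided α = 0.05, power 80%, 3 per group; and a quoted range of 0.8 to 1.9 for the within-subject SD of VO₂max. From Section 4: 20 screened, 10 donating, up to 25% failing on VO₂max. The allocation ratio is not stated; 1:1 is assumed because the power statement gives equal groups.

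**1. Screening.**
- Left after a 25% loss: 20 × (1 − 0.25) = 15. Because the rate is an upper bound, this is the minimum left after that loss.
- Screened to obtain 10 at 25%: 10 / 0.75 = 13.3, so 14.
- Total loss implied by 20 to 10: 1 − 10/20 = 50%.
- Further loss needed after the 25%: 1 − 10/15 = one third. The plan gives no rate for this.

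**2. The plan's own power figure.** With the normal approximation,

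n per group = 2 × [σ(1.960 + 0.842)/δ]² = 2 × [1.5 × 2.802/3.5]² = 2.88, rounded up to 3.

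Power at n = 3: δ/(σ√(2/n)) = 3.5/(1.5 × √(2/3)) = 2.858, and Φ(2.858 − 1.960) = 81.5%. So the stated 3 per group and 80% are reproduced.

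**3. Power under the planned t-test.** The noncentrality parameter is δ/(σ√(1/n₁ + 1/n₂)), with n₁ + n₂ − 2 degrees of freedom. At 3 v 3 the noncentrality is again 2.858, but the critical value on 4 degrees of freedom is 2.776 instead of 1.960. At 5 v 5 the noncentrality is 3.689 and the critical value on 8 degrees of freedom is 2.306.

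| Randomised | Power, SD 1.5 | Power, SD 1.9 |
|---|---|---|
| 3 v 3 | 58.0% | 40.7% |
| 4 v 4 | 78.4% | 58.8% |
| 5 v 5 | 89.6% | 72.3% |
| 7 v 8 | 98.6% | 90.8% |
| 10 v 10 | 99.8% | 97.3% |

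The t-test first reaches 80% at 5 per group with SD 1.5. The 1.9 column is a sensitivity case that takes the top of the quoted range as the SD of the change.

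**4. The rank-sum fallback.** With 3 v 3 there are 20 equally likely arrangements under the null hypothesis, so the smallest two-sided p-value is 2/20 = 0.10. At that size the test cannot reach 0.05 whatever the data.

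**5. What repeated testing would do.** In a simulation of 200,000 null trials, with unadjusted two-sided 0.05 t-tests at 3 and again at 5 per arm, the type I error was 8.3%. The plan does not describe such looks; the figure only shows the size of the risk if they were made.

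**The case against.** The strongest reply is that the numbers count different things and form a funnel: 20 consented and screened, 10 donating, and 3 per group as a minimum that the plan says it will exceed. Section 7 supports this by counting screen failures among those who enrol. The reply largely stands. A reader might infer that the plan gives three incompatible sample sizes, and the documents do not support that; only reading the 20 as qualified or randomised subjects contradicts the 10. What remains is that the opening eligibility text uses the same word for qualified volunteers, and nothing in the plan settles which meaning applies.

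Similarly, the 25% covers low VO₂max only. Haemoglobin, blood volume, QTc and other exclusions, or withdrawal, could take 15 to 10, and underestimating the yield is the safer direction for recruitment. So the arithmetic is unexplained rather than proven wrong. But the sentence rests the 10 on the 25% alone.

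A reader might also infer that power is undefined. It is not: Section 9 states it for one size and gives the inputs for any other. The fault is that the stated value does not hold for the planned test, and none is given for the number likely to be randomised.

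Finally, a reader might infer that the sentence about more patients means repeated testing and an inflated type I error. No section describes an interim analysis or a repeated test, and the sentence can be read as a margin set in advance. Extending on blinded variability alone would leave the error close to 5%. The inflation is therefore only a conditional risk that the open wording does not rule out.

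**Conclusion.** The point holds in this form: the sample-size figures are unreconciled and their stated basis fails. A failure rate of up to 25% gives at least 15 from 20, not 10; the 50% attrition is unexplained; and the number to be randomised is not stated. The claimed 80% power at 3 per group is 58% under the planned two-sided t-test, a shortfall of about 22 percentage points.

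The consequence is limited if the 10 donors are all randomised 5 v 5, since power is then 90% at SD 1.5, although it falls to 72% at SD 1.9. These figures rest on the plan's difference of 3.5, normal data with equal variances and 1:1 allocation. The design is not invalidated, but the plan should be corrected because its only power statement is wrong for its own test and its end point for recruitment is open.

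**What to change.** - State separately the numbers to be screened, to donate, and to be randomised per arm, for example 20 screened and 10 randomised (5 per arm), and state the allocation ratio. Use the same numbers under Study size, in Inclusion Criteria iii and in Section 9, and say whether the 20 enrolled are the 20 screened.
- Give the all-cause attrition that takes 20 to 10, including any loss between donation and Day 14. If 25% is meant to be the total loss, correct the number screened to 14.
- Replace the claim of 80% power at 3 per group with power from the t distribution at the randomised number (90% for 5 v 5 at SD 1.5), with a sensitivity figure for a larger SD.
- Replace the sentence about studying more patients with a fixed number and a statement that the primary test is done once, after that number has completed.

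The cost is protocol wording only. The one thing given up is the freedom to add subjects informally.

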VISIT A (– Screening) Written informed consent will be obtained from subjects who respond to an IRB-approved advertisement/flyer and fulfill eligibility requirements. The following video will help explain the study: vimeo.com/167291799. Individuals who respond to an IRB approved advertisement/flyer (uploaded to eIRB) will be given information about the study and asked to read an IRB approved consent form. An investigator or designee will obtain written informed consent from each individual participating in this study, after adequate explanation of the methods, objectives, and potential hazards of the study. The investigator or designee will also explain to the subjects that they are completely free to refuse to enter the study and free to withdraw from it at any time. A copy of the signed consent form will be given to the subject and will be shared with The Blood Connection to ensure proper labeling of autologous units.

After subjects have provided written informed consent, they will be asked to answer several questions in 2 written questionnaires (uploaded to eIRB) in order to confirm that they are eligible to donate blood. These questions are similar to those routinely asked to people prior to a blood donation. These are focused upon keeping the risks of blood donation to the lowest possible level. Subject will undergo screening lab tests for baseline hemoglobin, sickle cell trait, serum pregnancy tests only for women of child-bearing potential, ECG, exercise test. Subject will receive a phone confirmation from the investigator or delegated research staff after review of the screening lab results. Subject will bring a copy of the signed consent form to The Blood Connection if qualified.

VISIT B (Day 0 – Blood donation) The Blood Connection (TBC), Raleigh, NC, is registered and licensed by the US FDA and accredited by the American Association of Blood Banks (AABB) to manufacture RBCs and other blood products. Two units of blood will be withdrawn from each subject according to standards for double, AS-3, apheresis units, and will be marked for autologous donation, and purchased by Duke Transfusion Services, as arranged with the medical director of TBC ([name]). RBC handling and storage will meet FDA and AABB standards; units will be stored with Duke Transfusion Services c/o [name].

VISIT C (Day 14 – “Anemic” VO₂ max, Transfusion (Tx) and “post-Tx” VO₂max)

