Small amount of blood [3 lavender topped tubes] will be collected from subject to test for hemoglobin, type & screen and 1 cross match to verify the donated blood received from

RESEARCH Summary

Pro00078468

NCT03089047

PI: [name]

The Blood Connection belongs to the same subject who arrives at the appointed date at Duke facility

Anemic VO₂max

Three minutes of resting baseline measures will be recorded before the start of exercise. The subject will then begin to pedal the cycle ergometer at a cadence of 75 rpm. Resistance will be manually set according to a standardized, progressive protocol. A rating of perceived exertion (RPE) will be obtained at the end of each exercise stage. Vital signs will be recorded every 3 minutes, and ECG monitoring will be continuous. Exercise will be terminated when the subject reaches volitional fatigue. VO₂max will be reported as the highest oxygen consumption averaged over two 30-second periods, which typically occurs in the last stage of the progressive maximal exercise test. Maximum heart rate will be the heart rate at or near VO₂max. To minimize variability in VO₂max testing procedures, the same 2 facilitators (an engineer/technician and a research staff) will be present at every test. Radial arterial access will be obtained for cardiac output monitoring (LiDCO pulse contour analysis) at this visit.

Tx and post-Tx VO₂max

Duke Transfusion Services will randomize each subject to receive 2 units of standard PRBCs or rejRBCs over 120 minutes using a standard infusion pump. All units will be washed to equalize the transfusion volumes; rejuvenation includes a mandatory washing step. Rejuvenation of donated blood will be done according to the procedures in the labeling of the Rejuvesol product. Vital signs will be monitored and recorded every 15 minutes. After a total 4-hour rest after completing the first VO₂max testing, and a light snack, the exercise test will be repeated.

Laboratory testing: The p50 will be measured in one of the blood units transfused and in the subject before the exercise test. Radial arterial access will be obtained for serial cardiac output monitoring (LiDCO Pulse Contour Analysis, LiDCO Products, London, UK), arterial blood gas analysis and lactate measurement before and after transfusion, and after exercise testing. Final blood collected for a hemoglobin level will be done at the conclusion of blood transfusion. This is the final visit and participation is completed.

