Rejuvenated RBC units will be prepared according to manufacturer's protocols, which include a mandatory washing step on an approved cell-washing device.¹⁶ The manufacturer reports no adverse effects resulting from use of Rejuvesol® per manufacturer's instructions, and further notes that the risk of toxicity due to Rejuvesol® solution components is low since all solution components are common endogenous chemicals that are normally metabolized *in vivo*.¹⁶

6. Risk/Benefit Assessment:

- 1) Risks associated with venipuncture: Venipuncture results in momentary discomfort. Infection, excess bleeding, clotting, or fainting is also possible, although unlikely. Phlebotomy performed for blood donation has complications including hematomas, nerve injury, thrombophlebitis, arterial puncture, and compartment syndrome. Excluding the blood collected at The Blood Connection an additional 110 ml of blood will be withdrawn from the subject over the screening period through Study Day 14.
- 2) Risks associated with blood donation⁵: Approximately 3.5% of all donations report an adverse reaction, the majority of which are mild and self-limiting, with less than 1:3,400 blood donors seeking medical care post-donation. Vasovagal reactions (faintness or loss of consciousness) are the most common reactions, with less than 0.01% of reported reactions resulting in fainting with injury. There is a 2% risk of citrate toxicity (tingling sensation, dizziness, muscle cramping) when undergoing apheresis double red cell collections. Nausea, vomiting, and post-donation fatigue are also reported. To minimize the chances of this occurring, per standard TBC procedures, all volunteers will be offered some food and liquid after donation and will be encouraged to sit for 30 minutes after donating. Additionally, fewer donor adverse events are seen with double red cell collection due to the saline blood volume replacement they receive. In addition, consistent with The Blood Connection normal routine procedures, blood will only be collected from subjects with a hemoglobin of at least 12.5 g/dL.

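### Pregnancy is an exclusion, but it is tested only at screening, with no time limit to donation and no repeat before the Day 0 or Day 14 procedures

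*Combined protocol and SAP*

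**What the plan says.** All references are to the combined protocol and SAP.

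- **Eligibility (Section 4).** Inclusion criterion i reads "Healthy male or female", and criterion ii sets the age range at 18 to 40. Pregnancy is exclusion ix, a one-word entry with no timing attached.
- **Visit A (screening).** The pregnancy test appears here and nowhere else: "Subject will undergo screening lab tests for baseline hemoglobin, sickle cell trait, serum pregnancy tests only for women of child-bearing potential, ECG, exercise test". The visit table gives Visit A no day number. The next step is a call: "Subject will receive a phone confirmation from the investigator or delegated research staff after review of the screening lab results". No time limit is attached to that call or to the donation that follows.
- **Visit B (Day 0).** The table entry is "Donate 2 units of PRBCs by autologous apheresis". The donation-day check that the protocol states is in Section 6, item 2: "blood will only be collected from subjects with a hemoglobin of at least 12.5 g/dL".
- **Visit C (Day 14).** The sample taken before exercise "will be collected from subject to test for hemoglobin, type & screen and 1 cross match". Section 5 adds a radial arterial catheter, arterial gases, lactate and lithium-dilution cardiac output on the same day. Two maximal exercise tests are performed, with a two-unit transfusion between them.

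**The concern.** Pregnancy status can change after screening, yet the plan looks at it once, before donation and before everything done on Day 14. A woman who conceives after Visit A, or who is tested there too early for detection, could go through donation and the Day 14 procedures without any protocol test identifying the pregnancy. No protocol deviation would be recorded.

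These are healthy volunteers, so no therapeutic benefit offsets a missed exclusion. The plan already rechecks another screening finding: hemoglobin is measured at the blood center and again on Day 14. It also provides for a subject who reports fever within two days of donation (Section 6, item 4a). Pregnancy has no comparable step. The visible text also contains no contraception requirement and no rule for a pregnancy found after screening.

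**Working it through.** The plan gives no figure to reproduce. The check sets the visit schedule against exclusion ix and then works out the age of the test result at each exposure.

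**Step 1: schedule against exclusion.**

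| Visit | Pregnancy test stated | Study procedures |
|---|---|---|
| A (no day number) | Serum test, women of child-bearing potential | Screening maximal exercise test |
| B (Day 0) | None | Two-unit red cell apheresis |
| C (Day 14) | None | Arterial catheter, about two lithium injections, two maximal exercise tests, two-unit transfusion |

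**Step 2: age of the result.** Let w be the number of days from Visit A to Day 0.

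- Age at donation = w.
- Age at the Day 14 procedures = w + 14.

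The documents give no value for w. The values below are assumptions, used only to show the range.

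| Assumed w (days) | Age at Day 0 | Age at Day 14 |
|---|---|---|
| 1 | 1 | 15 |
| 7 | 7 | 21 |
| 14 | 14 | 28 |
| 28 | 28 | 42 |
| 56 | 56 | 70 |

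Screening results are reviewed before donation, so w cannot be negative and the Day 14 figure is at least 14 days. No maximum follows from the text.

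**Step 3: how many women could be affected.** Section 4 expects 10 donors from 20 screened. Eligible women need a calculated blood volume of at least 4,500 mL, a BMI of no more than 30 and a screening hemoglobin of at least 13.3 g/dL. The protocol's formula for women is 0.005835 × H³ + 15 × W + 183, with H in inches and W in pounds.

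- H = 66: 0.005835 × 287,496 = 1,677.5, so W must be at least (4,500 − 183 − 1,677.5) / 15 = 176 lb. BMI = 703 × 176 / 66² = 28.4, which is eligible.
- H = 65: 0.005835 × 274,625 = 1,602.4, so W must be at least (4,500 − 183 − 1,602.4) / 15 = 181 lb. BMI = 703 × 181 / 65² = 30.1, which is excluded.

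Women of about 65 inches or less are therefore effectively ruled out. Women can still qualify, but probably only a few will.

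**The case against.** The strongest reply has four parts.

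**Unseen safeguards.** Two questionnaires are held outside this document. The blood center follows its own standard procedures, and Section 6, item 4a says that allogeneic donor criteria apply. Any of these might ask about pregnancy. This stands as a caution about Day 0: the documents neither confirm nor rule out such a check. It does not answer Day 14, because none of these sources is placed there.

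**An entry criterion checked at entry is not a contradiction.** This is also correct. No two passages conflict. The gap is between the exclusion's evident purpose and the timing of its only test.

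**Few women are involved.** This is true, as the blood-volume arithmetic shows. It limits how often the gap could matter, and it also keeps the remedy cheap.

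**Stronger readings do not follow.** A reader might infer any of the following, and the documents do not support them.

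- *That exclusion ix ceases to apply after screening.* The criterion has no time limit, so a known pregnancy still excludes. What is missing is verification.
- *That every study exposure comes after Visit A.* Visit A itself includes a maximal exercise test. The protocol does not say whether the pregnancy result must be known before it.
- *That screening hemoglobin goes equally stale.* It is measured again at donation and on Day 14.
- *That an old screening VO₂max biases the trial.* The primary VO₂max contrast uses two Day 14 tests, and randomization is on Day 14, so earlier drift in fitness cannot bias the group comparison. At most it adds minor noise to the secondary change from baseline, and to baseline VO₂max as a regression covariate. The documents do not allow its size to be estimated.

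**Conclusion.** The point holds as a participant-safety and eligibility gap. The protocol schedules pregnancy testing at one visit, sets no limit on the time from that visit to donation, and lists no repeat at Visit B or Visit C. Pregnancy status is therefore not verified, on the visible text, at red cell removal. The result is at least 14 days old, with no upper bound, at the Day 14 procedures.

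The conclusion rests on the visible text listing all the pregnancy testing that is planned. For Day 0 it could be softened by the questionnaires or the blood center's procedures. For Day 14 nothing in the documents suggests a check. The number of women exposed to the gap is likely to be small. There is no consequence for sample size, power or the primary analysis. The change is worth making because it is cheap and closes a gap in an exclusion that the protocol itself chose.

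**What to change.** Reconcile exclusion ix with the visit schedule.

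1. State a maximum interval from Visit A to Day 0, with its length set by the investigator, and say which screening items are repeated if it lapses.
2. Re-verify pregnancy status in women of child-bearing potential before the Day 0 procedures and again before the Day 14 procedures. If the questionnaires or the blood center already do this for Day 0, cite that step in the protocol.
3. Have the investigator state what follows a positive result at either point, including one found after donation. This review does not propose that rule.

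The cost is one or two inexpensive tests in a few women and an occasional repeat screening visit. Blood is already drawn before exercise on Day 14, but into lavender-topped tubes, so a serum test may need one extra tube.
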